6.7 Withdrawal Visit

Subjects will be exited from the experimental component of the research protocol following the first visit or following visit 6. All subjects will be exited from the study and assessed by the General and Oral Health Center dental personnel for additional periodontal care within the General and Oral Health Center or for referral to another dental clinic as appropriate.

6.8 Unscheduled Visit

Unscheduled study visits will be documented in the electronic data capturing tool (CDART 2.0 which is the clinical research data management system designed and developed by UNC's Collaborative Studies Coordinating Center (CSCC) and NC TraCS), utilized for this research study. This documentation will be recorded in the clinical notes section of the participant and will include date of visit, reason for visit, procedures performed during the visit, if a follow up visit will be required and the initials of the study staff recording the clinical note.

7 STUDY PROCEDURES/EVALUATIONS

7.1 Study Procedures/Evaluations

Prior to the first subject study visit, study examiner(s) will be trained and calibrated for accuracy and repeatability in using the UNC Modified Gingival Index (GI); Loe and Sillness, UNC Modified Plaque Index (Green & Vermillion), periodontal pocket depths, and clinical attachment levels using a periodontal probe. All examiners have a kappa > 0.90 for all calibration sessions.

Calibration training will be conducted on an annual basis according to the guidelines set forth in this document including: Periodontal determination of plaque (PI), gingival inflammation (GI), gingival bleeding (BOP), pocket probing depths (PD) and clinical attachment levels (CAL). These parameters are customarily used in clinical dental studies to measure the disease status of gingivitis and periodontitis. Probe penetration and depth may vary with the degree of inflammation, probing force, angulation, position and instrument tip diameter.

Other confounding factors include patient discomfort, accuracy of probe markings, anatomical differences in tooth crown and roots, and technique variability within and between examiners. Thus, all of these measurements are important to consider in periodontal clinical studies and this training session is designed to minimize the inter-examiner variance.

Stent-Induced Biofilm Overgrowth (SIBO) Model

A customized stent will be fabricated for each subject. The stent will be fabricated to resemble an acrylic mouth-guard but extended to cover approximately 2mm over gingival margins. The stent will form a seal and rest on the gingiva, but will be relieved on the tooth and tissue side except for the occlusal surfaces to avoid disturbing plaque or gingival tissues. The acrylic stent will cover the area in one sextant where no brushing and flossing teeth is to occur during 21 days. The acrylic stent will be worn only during tooth brushing. Subjects will be monitored for safety every week and after the induction of experimental biofilm overgrowth through 21 days.

The SIBO model only induces a transient gingival inflammation without any addition of further periodontal attachment loss. The model was previously used and results support the safety of the model with no further loss of periodontal attachment (47-49). If test sites demonstrate a clinical attachment loss of more than 2 mm during the study, subjects will be removed from the study and receive rescue therapy (Scaling and Root Planing) at the same day of the visit. Clinical attachment loss will be automatically calculated by the entry software used in the study (Dental ToolKit) and compared longitudinally to the baseline clinical attachment level measurement. Previous publications from our group

demonstrated that the SIBO model is safe by having no subjects required to withdraw from previous SIBO studies due to clinical attachment loss (47-49).

Clinical Assessments and Data Collection

UNC Modified Gingival Index (GI), Loe and Silness

Full mouth gingival scores shall be visually assessed by segmenting marginal and papillary units, 6 sites per tooth: distobuccal, buccal, mesiobuccal and distolingual, lingual, mesiolingual surfaces.

0 = Normal gingiva

1 = Mild inflammation; slight change in color, slight edema. No bleeding on probing.

2 = Moderate inflammation:redness, edema, and glazing. Bleeding on probing

3= Severe inflammation; marked redness and edema. Ulceration. Tendency for spontaneous bleeding.

UNC Modified Plaque Index (Green & Vermillion)

Full mouth plaque assessment shall be assessed using the UNC Modified Plaque Index (Greene and Vermillion). Plaque scores shall be visually assessed at **6 sites per tooth** (distobuccal, buccal, mesiobuccal and distolingual, lingual, mesiolingual surfaces) on a scale of 0-3.

0 =No debris or stain present on the clinical crown.

1 =Soft debris covering not more than 1/3 of the clinical crown (cervical 3rd), or presence of extrinsic stains without other debris regardless of surface area covered.

2 =Soft debris covering more than 1/3, but not more than 2/3 (middle 3rd) of the clinical crown.

3 =Soft debris covering more than 2/3 of the clinical crown

Pocket depth (PD): Linear distance from the gingival margin (GM) to base of the pocket. If a PD reading falls between two millimeter readings, the rule shall be to round down and the lower of the two readings will be recorded.

Bleeding on Probing (BOP): Presence or absence of bleeding to manual probing recorded as a dichotomous variable.

0- No bleeding within 10 seconds after probing.

1- Bleeding within 10 seconds after probing.

Clinical Attachment Level (CAL): Linear distance from the cemento-enamel junction (CEJ) to base of the pocket. If a CAL reading falls between two millimeter readings, the rule shall be to round down and the lower of the two readings will be recorded.

7.2 Laboratory Procedures/Evaluations

Dental plaque samples and gingival tissue samples will be collected at the dental research clinic of the UNC School of Dentistry (General and Oral Health Center). All bar coded de-identified biological samples will be transported to the laboratory of the principal investigator for processing with a chain of custody recording for each sample. All information collected for this study will only be used for the study, and not as part of another study. Additional grant request may be submitted in the future to complete additional analyses on stored biological specimens.

All measurements will be conducted using standard techniques that will be carried out in the investigator's laboratory and in collaborations previously established by the investigator (Histology Research Core Facility, Microbiome Core Facility at UNC).

7.3 Study Specific Biospecimens

7.3.1 Specimen Collection Procedures

Specimen Collection Procedures

Plaque: The dental examiner will collect two separate, facial, sublingual plaque samples, from the interdental sulculs of the teeth that are selected for a gingival biopsy .Dental implants will not be considered for plaque samples. Subgingival plaque samples will be obtained with a sterile Gracey dental curette. The curette tip shall be inserted into to the depth of the sulcus and plaque shall be collected in a single coronal stroke movement. After plaque collection, the curette is then placed in an Eppendorf tube containing 500 ul of TE buffer (10mM Tris-HCl, 0.1 mM EDTA, pH 7.6) and shaken for a few seconds to release the bacterial cells from the curette into the solution. The plaque sample can then remain at the clinic until the end of the day, when all samples are taken to the laboratory, where they are stored at -80 °C for later bacterial microbiological analysis. All samples will be taken to the UNC Cytokine Analysis Lab for validation of collection and storage.

We will evaluate the microbial content determined by sequencing the V3-V4 variable region of 16S rRNA gene using next generation sequencing (50). The bacterial diversity and relative abundance (% of total reads) of each genus and taxon will be evaluated using the QIIME pipeline analysis on the 16S rRNA Illumina sequencing with references databases (SILVA, Greengenes and the Human Oral Microbiome Database). This is a high-throughput state-of-the art technology (50, 51).

Gingival Tissue/Biopsy: Biopsy samples of gingival tissues will be collected from all individuals at baseline and 21-days of biofilm-overgrowth. A trained dentist will use a scalpel blade to collect 2 biopsy samples per subject for a total of 128 samples. Samples will be obtained using topical and local anesthesia. Each biopsy shall be ≤ 0.5 cm thick. Biopsies will only be collected from the papillae of posterior teeth. The scalpel blade shall be oriented in an inverse bevel direction to capture the base of the periodontal pocket or gingival sulcus. Each biopsy will contain oral epithelium, gingival connective tissues and loosely adherent cells lining the periodontal pocket. Papillae height will be retained by using vertical mattress suture technique, minimizing facial reduction, and coronal reposition of the flap. The biopsy wound will be undermined with minimal flap reflection and closed with a suture. Post-operative instructions, including placing ice over the surgical area and avoiding hot liquids for the remainder of the day, will be given to the subject.

Gingival biopsy samples will be bi-sectioned for immunohistochemistry/immunofluorescence imaging and mRNA expression.

1. For **RNA** extraction, samples will be immediately placed in RNeasy[®] (Ambion Inc.) which is an aqueous, non-toxic tissue storage reagent that rapidly permeates tissue to stabilize and protect cellular RNA *in situ* in unfrozen specimens. Samples will be placed in a microfuge tube containing ~1ml of RNeasy and kept at 4°C overnight, then RNeasy is removed. Samples will be stored at -80°C until used for analysis.
2. For **Immunohistochemistry/Immunofluorescence**, samples will be fixed in 4% paraformaldehyde and stored at -20°C for 24 hours and then placed in 70% ethanol for further analysis.

7.3.2 Specimen Preparation, Handling, and Storage

All biological samples are collected into pre-labeled barcoded vials for laboratory processing. Clinical data are collected and stripped of all subject identifiers and provided a bar-coded ID that link the subject's clinical data to the study visit, examiner, date and dataset. Biological samples are analyzed by the laboratory in a blinded manner and at the data closeout the ID links are established to connect the clinical data to the laboratory data. None of that data contains any patient identifiers. Identification design uses a barcode that includes the study ID, subject ID, visit ID and biological specimen ID.

Example barcode:

- "ITS" is the acronym that identifies the specific IRB approved research study.
- "1001" is the subject identifier
- "03" is the visit ID (visit 3)

- “904” is the specific biological sample ID

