11 STATISTICAL CONSIDERATIONS

11.1 Study Hypotheses

The central hypothesis of this proposal is that IFI16 functions to attenuate the host response that drives periodontitis. We propose to investigate whether macrophage-derived IFI16 expression modulates tissue inflammation via AIM2. Human tissues will be used for confirming results generated by the principal investigator from in vitro and in vivo models that show high expression of AIM2 and IFI16 under inflammatory conditions (4). Better characterization of the cellular and molecular biology of inflammasomes will help identify important potential therapeutic targets for the treatment and prevention of periodontal diseases. The following “hypothesis” corresponding to Study Objective 1 (section 3.1) is:

Primary hypotheses corresponding to the second study objective **will be tested**:

- 1a. There will be a temporal change in expression of AIM2 (mRNA fold change and percentage of positive cells for histological analysis) induced by SIBO in healthy and severe periodontitis subjects
- 1b. There will be a temporal change in expression of IFI16 (mRNA fold change and percentage of cells for histological analysis) induced by SIBO in healthy and severe periodontitis subjects
- 1c. There will be differences in temporal changes in expression of AIM2 (mRNA fold change and percentage of cells for histological analysis) induced by SIBO between healthy and severe periodontitis subjects
- 1d. There will be differences in temporal changes in expression of IFI16 (mRNA fold change and percentage of cells for histological analysis) induced by SIBO between healthy and severe periodontitis subjects

Exploratory hypotheses corresponding to the second study objective will be assessed:

- 2a. The stent-induced change in expression of protein AIM2 will correlate with differentially expressed (between healthy and severe periodontitis subjects) periodontal pathogens identified by 16S rDNA (% of total reads) at baseline (visit 2)
- 2b. The stent-induced change in expression of protein IFI16 will correlate with differentially expressed (between healthy and severe periodontitis subjects) periodontal pathogens identified by 16S rDNA (% of total reads) at baseline (visit 2)
- 2c. The stent-induced change in expression of protein AIM2 will correlate with the temporal change in periodontal pathogens identified by 16S rDNA (% of total reads)

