11.2 Sample Size Considerations

In order to evaluate the expression of IFI16 and AIM2 in subjects, 72 (36 subjects/group) will be recruited from the patients, students, staff and general population at the University of North Carolina-School of Dentistry. We will enroll 72 subjects to accommodate a 10% drop-out rate. Individuals with healthy tissues and severe periodontitis will be enrolled based on Morelli et al 2017 (1). Sample size calculations are based, in part, on preliminary cross-sectional (non-SIBO experiment) data on expression levels of Aim2 from immunohistochemistry reported in Xue et al. (2015; Table 3) who reported statistically significant differences in healthy (n=10; mean=0.50; s.d.=0.14) and severe periodontitis (n=10; 0.97; s.d.=0.27) subjects with respect to AIM2 expression from immunohistochemical analyses. For the first study objective (section 3.1), there will be 99% power to detect differences in AIM2 and IFI16 expressions at Visit 2 between healthy and severe periodontitis at these levels using two-sided t-tests at the 0.05 significance level. When comparing change in AIM2 expression levels from visit 2 to visit 5, assumptions of a common standard deviation of 0.25 and an intra-subject correlation of 0.40 across the two time points indicate that power will be at least 80% to determine differences in change between healthy and severe periodontitis subjects that are as small as 0.40; in a worst case (but not realistic) scenario, an intra-subject correlation of 0 would give 80% power to detect differences in temporal change that are as small as 0.50. Xue et al (2015; Figure 1c) found no statistically significant cross-sectional differences between healthy and severe periodontitis subjects with respect to mRNA expression of AIM2; they did not report this data numerically precluding power analysis.

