11.3 Final Analysis Plan

1) (Primary) compare the expression (fold-change relative to baseline) of AIM2 and IFI16 between healthy (PPC-A, PPC-B) and severe periodontitis (PPC-E, PPC-G) subjects during an acute inflammatory response using the stent-induced biofilm overgrowth model

3) (Exploratory) correlate the expression of these proteins with periodontal pathogens

For the primary hypotheses involving gingival tissue samples, univariate and multivariate nonparametric testing procedures for SIBO experiments (Preisser, Sen and Offenbacher, 2011) will be utilized. In particular, a multivariate Wilcoxon Signed Rank test will use all available data to jointly test for changes in AIM2 and IFI16 expression levels over time (visit 2 to visit 5). If the overall multivariate test is statistically significant at the 0.05 level, then univariate Wilcoxon Signed Rank tests will be applied to AIM2 and IFI16 proteins individually. Similar procedures will be applied for expression levels from mRNA and from immunohistochemistry. Additionally, multivariate and univariate Wilcoxon Rank Sum Tests will be applied at the 0.05 significance level to compare SIBO-induced temporal change in Aim2 and IFI16 expression levels between healthy and severe periodontitis subjects.

Parametric statistical procedures will be used to summarize and test periodontal clinical measurements related to secondary hypotheses. Means and their 95% confidence intervals will be used to summarize measurements at each time point in healthy and severe periodontitis subjects. As these measurements will be collected at visits 2, 3, 4 and 5, linear mixed models will be used to assess change over time within groups and differences in change over time between healthy and severe periodontitis groups.

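### Section 7.3.2 promises blinded laboratory analysis without naming what is masked and puts subject and visit in the specimen code; if readable on the slides, visit is unmasked for the IHC part of 1a/1b

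*Combined protocol and SAP*

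**What the plan says.** - **Blinding (7.3.2).** "Biological samples are analyzed by the laboratory in a blinded manner and at the data closeout the ID links are established". The sentence goes on to say that these links join the clinical data to the laboratory data. It does not name the factors that are masked.
- **Specimen code (7.3.2).** "Identification design uses a barcode that includes the study ID, subject ID, visit ID and biological specimen ID". The worked example shows the visit field as the plain visit number. Disease group is not a field.
- **Where the code sits (7.3.2).** "All biological samples are collected into pre-labeled barcoded vials for laboratory processing".
- **Tissue time points (7.3.1, Appendix I).** "Biopsy samples of gingival tissues will be collected from all individuals at baseline and 21-days of biofilm-overgrowth". These are visits 2 and 5, and no other visit has a biopsy.
- **Endpoint (11.1).** Hypothesis 1a reads "There will be a temporal change in expression of AIM2 (mRNA fold change and percentage of positive cells for histological analysis) induced by SIBO"; 1b is the same for IFI16. Hypotheses 1c and 1d compare the changes between healthy and severe periodontitis subjects.
- **Test (11.3).** "a multivariate Wilcoxon Signed Rank test will use all available data to jointly test for changes in AIM2 and IFI16 expression levels over time". Univariate signed-rank tests follow if the joint test is significant at 0.05. Rank-sum tests compare the groups.
- **Custody.** Samples go to the principal investigator's laboratory, with the histology core named as a collaborator (7.2). The study coordinator keeps the linkage to the specimen codes (12). SOPs and a Manual of Procedures are mentioned (13, 15.6) but are not part of these documents.

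**The concern.** With only two biopsy visits, the visit field is a complete before/after flag, and the subject field matches the two samples. Holding back the clinical link until closeout does not hide visit, because visit is already in the code.

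Hypotheses 1a and 1b are listed as primary, and their IHC part compares visit 2 with visit 5. If the reader knows the visit, a small systematic difference in scoring cannot be separated from a stent effect. The design has no internal check on this: the single day-21 biopsy comes from the stented area (6.5, Appendix II), so there is no unstented day-21 tissue to reveal a drift. Section 11.1 also states an expected direction, high expression of both markers under inflammation, and the calibration described in sections 7.1 and 13 covers clinical examiners, not slide readers.

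**Working it through.** **Step 1: what the text settles.**

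| Question | Answer in the documents |
|---|---|
| Is laboratory analysis blinded? | Yes (7.3.2) |
| Blinded to what? | Not stated; compatible with masking to clinical data only |
| Are subject and visit in the vial code? | Yes (7.3.2) |
| Is disease group in the code? | No |
| What label do IHC blocks and slides carry? | Not stated |
| Can the code be read without a scanner? | Not stated |
| Are cells counted by a person or by image analysis? | Not stated |
| Who reads the slides? | Investigator's laboratory or histology core (7.2); not settled |
| Is there a re-coding step? | None described; it may be in the SOPs or Manual of Procedures |

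**Step 2: which results are exposed.** Write a reader's drift as a constant d added to visit-5 scores.

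- 1a/1b: observed change = true change + d, so d goes straight into the signed-rank test.
- 1c/1d: difference in change = (severe + d) − (healthy + d), so a common d cancels.
- qRT-PCR depends less on a reader's judgement, so the IHC percentage of positive cells is the exposed part.

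**Step 3: what a drift would do (illustration only).** The plan gives no figure on this point to reproduce, and no IHC reliability figure.

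Inputs from section 11.2: "assumptions of a common standard deviation of 0.25 and an intra-subject correlation of 0.40 across the two time points", with zero correlation as its lower case ("in a worst case (but not realistic) scenario, an intra-subject correlation of 0 would give 80% power"). The pairs come from the 128 biopsies in 7.3.1: 128/2 = 64 pairs, or 32 per group. The plan does not say whether groups are pooled for 1a/1b, so both sizes are shown.

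Assumed: d = 0.025 or 0.05 (one-tenth or one-fifth of the SD), normal changes, no true change, and that the planning SD applies to the IHC score.

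SD of change = 0.25 × √(2(1 − ρ)):

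- ρ = 0: 0.25 × √2 = 0.354; SE = 0.354/√32 = 0.0625, or 0.354/√64 = 0.0442.
- ρ = 0.40: 0.25 × √1.2 = 0.274; SE = 0.274/√32 = 0.0484, or 0.274/√64 = 0.0342.

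A drift of 0.05 is therefore 0.05/0.0625 = 0.80 to 0.05/0.0342 = 1.46 standard errors.

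Simulated rejection by the univariate signed-rank test (two-sided 0.05, exact critical values, 200,000 replicates):

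| ρ | Pairs | d = 0 | d = 0.025 | d = 0.05 |
|---|---|---|---|---|
| 0 | 32 | 4.9% | 6.7% | 11.8% |
| 0 | 64 | 4.9% | 8.5% | 19.4% |
| 0.40 | 32 | 4.9% | 7.7% | 16.5% |
| 0.40 | 64 | 5.0% | 10.8% | 29.2% |

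Planned sequence (joint two-marker test, then at least one univariate rejection), with the same drift in both markers, equal SDs, and an assumed between-marker correlation of 0 to 0.6:

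| Pairs | No drift | d = 0.025 | d = 0.05 |
|---|---|---|---|
| 32 | about 4% | about 5-8% | 9-19% |
| 64 | about 4% | about 7-12% | 17-38% |

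The 38% needs pooled groups, ρ = 0.40, uncorrelated markers and the larger drift in both markers.

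Rank-sum test for 1c/1d, 32 against 32, common drift of 0.05: 5.2% (ρ = 0) and 4.7% (ρ = 0.40), so unaffected.

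**The case against.** A reader might infer that section 7.3.2 contradicts itself, or that blinding to visit is a promise the code breaks. The text does not support either. The blinding sentence is tied to clinical links made at closeout and never names visit, so a visit field is compatible with it. That objection stands: the gap is in the scope of the blinding.

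The code is described on collection vials, not on slides. It is called a barcode, and section 15.2 describes scanning of bar-coded data, so its fields may not be readable by eye. The worked example uses visit 3, when no specimen is taken, so it shows format only. Cells may be counted by image analysis. Section 12 already places the code linkage with the coordinator, and slide labelling is ordinary content for SOPs. All of this stands, and it makes the consequence conditional. It does not close the gap, because the protocol gives no way to tell whether IHC reading is masked to visit.

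It can also be said that relabelling protects little, since inflamed tissue may be recognisable and the biopsy sites differ between visits: the baseline biopsy is outside the stented sextant (6.2), and the day-21 site is the stented tooth with the highest gingival index (6.5). Both limits are real. They limit what relabelling can achieve but are no reason to leave visit on the label.

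**Conclusion.** The point holds as a conditional weakness with a cheap remedy. It requires the code to be carried to the slides in readable form, a person to do the scoring, and no re-coding step elsewhere. The documents neither confirm nor exclude these.

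If they hold, the exposure is the IHC percentage of positive cells in 1a/1b. A reader might extend this to the between-group comparison, which is the primary objective in section 3.1. The documents do not support that: disease group is not in the code, and a drift equal in both groups leaves the rank-sum test at about 5%. A drift that differs by group would be another matter, but it would need the reader to recognise group by some other route.

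The simulated rates show what a drift of an assumed size would do. They are not evidence that a drift of either size is likely, and the plan does not equate its SD of 0.25 with the percentage of positive cells. Confidence is medium: the wording of 7.3.2 is clear, but the laboratory practice behind it is unknown.

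**What to change.** In section 7.3.2:

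1. State that IHC reading is masked to visit as well as to disease group.
2. Label IHC blocks and slides with a random accession number that has no subject or visit field, assigned by the study coordinator, who already holds the linkage.
3. Read slides from both visits and both groups in random mixed order, and state whether scoring is manual or automated.
4. Release the key only after IHC scores are locked.

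If an SOP already does this, a sentence citing it is enough.

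The cost is one relabelling step and a linkage list for material from about 128 biopsies; slides may outnumber biopsies because there are two markers. No participant visit or procedure is added. There is a small risk of mislabelling, which scanning the old and new codes together controls. The change does not hide inflammation visible in the tissue and does not remove the difference in biopsy site between visits.
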